6. DOSING DELAYS/DOSE MODIFICATIONS

Dose modifications for adverse events are per section 7.7.

7. ADVERSE EVENTS: LIST AND REPORTING REQUIREMENTS

7.1 Definition of Adverse Events

The International Conference on Harmonisation (ICH) Guideline for Good Clinical Practice (GCP) E6(R1) defines an AE as:

Any untoward medical occurrence in a patient or clinical investigation subject administered a pharmaceutical product and which does not necessarily have a causal relationship with this treatment. An AE can therefore be any unfavorable and unintended sign (including an abnormal laboratory finding), symptom, or disease temporally associated with the use of a medicinal product, whether or not considered related to the medicinal product.

An AE includes but is not limited to any clinically significant worsening of a subject's preexisting condition. An abnormal laboratory finding (including ECG finding) that requires medical intervention by the investigator, or a finding judged by the investigator as medically significant should be reported as an AE. If clinical sequelae are associated with a laboratory abnormality, the diagnosis or medical condition should be reported (eg, renal failure, hematuria) not the laboratory abnormality (eg, elevated creatinine, urine red blood cells increased). Abnormal laboratory values that are not, in the investigator's opinion, medically significant and do not require intervention should not be reported as AEs.

Adverse events may be treatment emergent (ie, occurring after initial receipt of investigational product) or nontreatment emergent. A nontreatment-emergent AE is any new sign or symptom, disease, or other untoward medical event that begins after written informed consent has been obtained but before the subject has received investigational product. Elective treatment or surgery or preplanned treatment or surgery (that was scheduled prior to the subject being enrolled into the study) for a documented pre-existing condition that did not worsen from baseline is not considered an AE (serious or nonserious). An untoward medical event occurring during the prescheduled elective procedure or routinely scheduled treatment should be recorded as an AE or SAE.

The investigator (or physician designee) is responsible for verifying and providing source documentation for all adverse events and assigning the attribution for all adverse events for subjects enrolled.

7.2 Definition of Serious Adverse Events

An SAE is any AE that:

- Results in death
- Is immediately life-threatening
- Requires inpatient hospitalization or prolongation of existing hospitalization
- Results in persistent or significant disability/incapacity
- Is a congenital anomaly/birth defect in offspring of the subject
- Is an important medical event that may jeopardize the subject or may require medical intervention to prevent one of the outcomes listed above

Medical or scientific judgment should be exercised in deciding whether expedited reporting is appropriate in this situation. Examples of medically important events are intensive treatment in an emergency room or at home for allergic bronchospasm, blood dyscrasias, or convulsions that do not result in hospitalizations; or development of drug dependency or drug abuse.

7.3 Definition of Adverse Events of Special Interest

An adverse event of special interest (AESI) is one of scientific and medical interest specific to understanding of the Investigational Product and may require close monitoring and rapid communication by the investigator to the supporting company. An AESI may be serious or non-serious. The rapid reporting of AESIs allows ongoing surveillance of these events in order to characterize and understand them in association with the use of this investigational product.

AESIs for durvalumab ±tremelimumab include but are not limited to events with a potential inflammatory or immune-mediated mechanism and which may require more frequent monitoring and/or interventions such as steroids, immunosuppressants and/or hormone replacement therapy. These AESIs are being closely monitored in clinical studies with durvalumab monotherapy and combination therapy. An immune-mediated adverse event (imAE) is defined as an AESI that is associated with drug exposure and is consistent with an immune-mediated mechanism of action and where there is no clear alternate etiology. Serologic, immunologic, and histologic (biopsy) data, as appropriate, should be used to support an imAE diagnosis. Appropriate efforts should be made to rule out neoplastic, infectious, metabolic, toxin, or other etiologic causes of the imAE.

If the Investigator has any questions in regards to an event being an imAE, the Investigator should promptly contact the Study Physician.

AESIs observed include:

- Fatigue / asthenia
- Pyrexia
- Diarrhea / Colitis

- Pneumonitis / Interstitial lung disease (ILD)
- ALT/AST increases / hepatitis / hepatotoxicity
- Neuropathy / neuromuscular toxicity (e.g. Guillain-Barré, and myasthenia gravis)
- Endocrinopathies (i.e. events of hypophysitis, hypopituitarism adrenal insufficiency, diabetes insipidus, hyper- and hypothyroidism and type I diabetes mellitus)
- Rash / Dermatitis
- Nephritis / Blood creatinine increases
- Pancreatitis (or labs suggestive of pancreatitis - increased serum lipase , increased serum amylase)
- Other inflammatory responses that are rare with a potential immune-mediated aetiology include, but are not limited to, myocarditis, pericarditis, and uveitis.
- AESI specifically related to Oleclumab (cohort B) include:::
 - Cardiac chest pain, transient ischemic attack, and thromboembolism
These are of interest due to the drug's risk of arterial calcifications, arterial ischemic disorder and thrombosis.
 - Edema
Oleclumab has potential risk of increased microvascular permeability, thus edema (pulmonary, peripheral, etc.) is considered an AESI. In the case of >= Grade 3 edema, doses should be omitted and therapy may be discontinued at the discretion of the investigator.
 - Immune complex disease
This may occur when human-anti-human antibodies are produced as a response to humanized mAb, resulting in formation and deposition of immune complexes in blood vessels, joints and glomeruli leading to symptomatic diseases (vasculitis, glomerulonephritis, arthritis, serum sickness, etc.). Subjects will be monitored clinically and with labs. If subjects experience a suspected immune-complex related AE, with confirmed presence of ADAs treatment will be discontinued and the condition will be managed based on standard of care.

In addition, infusion-related reactions and hypersensitivity/anaphylactic reactions with a different underlying pharmacological etiology are also considered AESIs.

Further information on these risks (e.g. presenting symptoms) can be found in the current version of the durvalumab and tremelimumab Investigator's Brochures. Additional information on the anticipated AE's for duvalumab + monalizumab combination therapy is noted in the current version of the monalizumab Investigator's Brochure (v.6). More specific guidelines for their evaluation and treatment are described in detail in the Dosing Modification

and Toxicity Management Guidelines (see Section 7.7). These guidelines have been prepared by the supporting company to assist the Investigator in the exercise of his/her clinical judgment in treating these types of toxicities. These guidelines apply to AEs considered causally related to the study drug/study regimen by the reporting investigator.

If new or worsening pulmonary symptoms (e.g. dyspnea) or radiological abnormality suggestive of pneumonitis/interstitial lung disease is observed, toxicity management as described in detail in the Dosing Modification and Toxicity Management Guidelines (see Table 7.7.1) will be applied. The results of the full diagnostic workup (including high-resolution computed tomography (HRCT), blood and sputum culture, hematological parameters etc) will be captured in the eCRF. It is strongly recommended to perform a full diagnostic workup, to exclude alternative causes such as lymphangitic carcinomatosis, infection, allergy, cardiogenic edema, or pulmonary hemorrhage. In the presence of confirmatory HRCT scans where other causes of respiratory symptoms have been excluded, a diagnosis of pneumonitis (ILD) should be considered and the Dosing Modification and Toxicity Management Guidelines should be followed.

7.3.1 Hepatic Function Abnormality

Hepatic function abnormality meeting the definition of Hy's law (ie, any increase in ALT or AST to greater than $3 \times$ ULN and concurrent increase in total bilirubin to be greater than $2 \times$ ULN) is considered an AESI. Concurrent findings are those that derive from a single blood draw or from separate blood draws taken within 8 days of each other. Follow-up investigations and inquiries will be initiated promptly by the investigational site to determine whether the findings are reproducible and/or whether there is objective evidence that clearly supports causation by a disease (eg, cholelithiasis and bile duct obstruction with distended gallbladder) or an agent other than the investigational product. Guidelines for management of subjects with hepatic function abnormality are outlined in section 7.7.

7.3.2 Pneumonitis

Adverse events of pneumonitis are also of interest for the supporting company, as pneumonitis has been observed with anti-PD-1 mAbs (but not with anti-PD-L1 mAbs). Initial work-up should include high-resolution CT scan, ruling out infection, and pulse oximetry. Pulmonary consultation is highly recommended. Guidelines for management of subjects with pneumonitis are outlined in Section 7.7.

7.3.3 Infusion Reactions

Adverse events of infusion reactions (also termed infusion-related reactions) are of special interest to the supporting company and are defined, for the purpose of this protocol, as all AEs occurring from the start of the study treatment infusion up to 48 hours after the infusion start time. For all infusion reactions, the eCRF should be completed as instructed in Section 7.4 and all SAEs should be reported to MedImmune Patient Safety as described in Section 7.5.

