5. More potent immunosuppressives should be considered for events not responding to systemic steroids (eg, infliximab, mycophenolate, etc).

If the investigator has any question in regards to an AE being an irAE, the investigator should immediately contact the medical monitor. Treatment modifications will not be required for AEs that are clearly not attributed to Durvalumab, tremelimumab, oleclumab or Monalizumab (such as an accident) or for laboratory abnormalities that are not deemed to be clinically significant.

Dose reductions of Durvalumab, tremelimumab, oleclumab or Monalizumab are not permitted.

Treatment modifications may be required for Durvalumab, tremelimumab, monalizumab, and oleclumab in the event of treatment-related toxicity. General guidelines regarding treatment modification are provided in Table 7.7.1 for all cohorts. In addition, management guidelines for adverse events of special interest (AESI) are detailed in Section 7.3. All toxicities will be graded according to NCI CTCAE v4.03 for cohort A and CTCAE v5.0 for cohorts B and C (CTCAE v5.0 is referenced in Table 7.7.1). In case of doubt, the investigator should consult with the medical monitor.

Table 7.7.1 Dosing Modification and Toxicity Management Guidelines

Dosing Modification and Toxicity Management Guidelines for Immune-Mediated, Infusion-Related, and Non-Immune-Mediated Reactions (Use for all Cohorts)

1 November 2017 (CTCAE Version 5.0)

General Considerations

Dose Modifications	Toxicity Management

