
Note: For Grade ≥ 3 asymptomatic amylase or lipase levels, hold study drug/study regimen, and if complete work up shows no evidence of pancreatitis, study drug/study regimen may be continued or resumed.
 
Note: Study drug/study regimen should be permanently discontinued in Grade 3 events with high likelihood for morbidity and/or mortality – e.g., myocarditis, or other similar events even if they are not currently noted in the guidelines. Similarly, consider whether study drug/study regimen should be permanently discontinued in Grade 2 events with high likelihood for morbidity and/or mortality – e.g., myocarditis, or other similar events even if they are not currently noted in the guidelines – when they do not rapidly improve to Grade <1 upon treatment with systemic steroids and following full taper
 
Note: There are some exceptions to permanent discontinuation of study drug for Grade 4 events (i.e., hyperthyroidism, hypothyroidism, Type 1 diabetes mellitus).
	
– when these events are not responding to systemic steroids.– With long-term steroid and other immunosuppressive use, consider need for Pneumocystis jirovecii pneumonia (PJP, formerly known as Pneumocystis carinii pneumonia) prophylaxis, gastrointestinal protection, and glucose monitoring.– Discontinuation of study drug/study regimen is not mandated for Grade 3/Grade 4 inflammatory reactions attributed to local tumor response (e.g., inflammatory reaction at sites of metastatic disease and lymph nodes). Continuation of study drug/study regimen in this situation should be based upon a benefit-risk analysis for that patient.

Specific Immune-Mediated Reactions

Adverse Events	Severity Grade of the Event (NCI CTCAE version5.0)	Dose Modifications	Toxicity Management
Pneumonitis/Interstitial Lung Disease (ILD)	Any Grade	General Guidance	For Any Grade:
			
 – Monitor patients for signs and symptoms of pneumonitis or ILD (new onset or worsening shortness of breath or cough). Patients should be evaluated with imaging and pulmonary function tests, including other diagnostic procedures as described below. – Initial work-up may include clinical evaluation, monitoring of oxygenation via pulse oximetry (resting and exertion), laboratory work-up, and high- resolution CT scan.

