Grade 1 or 2	
For Grade 1:
 
The infusion rate of study drug/study regimen may be decreased by 50% or temporarily interrupted until resolution of the event.
 
For Grade 2:
 
The infusion rate of study drug/study regimen may be decreased 50% or temporarily interrupted until resolution of the event.
 
Subsequent infusions may be given at 50% of the initial infusion rate.
	
For Grade 1 or 2:
 
 Acetaminophen and/or antihistamines may be administered per institutional standard at the discretion of the investigator. Consider premedication per institutional standard prior to subsequent doses. Steroids should not be used for routine premedication of Grade ≤ 2 infusion reactions.
Grade 3 or 4	
For Grade 3 or 4:
 
Permanently discontinue study drug/study regimen.
	
For Grade 3 or 4:
 
 Manage severe infusion-related reactions per institutional standards (eg, IM epinephrine, followed by IV diphenhydramine and ranitidine, and IV glucocorticoid).

PCP ; PO By mouth; T3 Triiodothyronine; T4 Thyroxine; TB Total bilirubin; TNF Tumor necrosis factor; TSH Thyroid-stimulating hormone; ULN Upper limit of normal.

CTCAE Common Terminology Criteria for Adverse Events; IM Intramuscular; IV Intravenous; NCI National Cancer Institute.

Table 7.7.1 Non-immune-mediated Reactions

Severity Grade of the Event (NCI CTCAE version 5.0)	Dose Modifications	Toxicity Management
Any Grade	Note: Dose modifications are not required for AEs not deemed to be related to study treatment (ie, events due to underlying disease) or for laboratory abnormalities not deemed to be clinically significant.	Treat accordingly, as per institutional standard.
Grade 1	No dose modifications.	Treat accordingly, as per institutional standard.
Grade 2	Hold study drug/study regimen until resolution to \leq Grade 1 or baseline.	Treat accordingly, as per institutional standard.
Grade 3	Hold study drug/study regimen until resolution to \leq Grade 1 or baseline. For AEs that downgrade to \leq Grade 2 within 7 days or resolve to \leq Grade 1 or baseline within 14 days, resume study drug/study regimen administration. Otherwise, discontinue study drug/study regimen.	Treat accordingly, as per institutional standard.

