8.1.5 Monitoring of Dose Administration

Subjects will be monitored prior to, during, and after infusion of Durvalumab, Tremelimumab, Oleclumab and Monalizumab.

Refer to Table 10.4 for monitoring schedule for vitals during dose administration for all cohorts.

In the event of Grade \leq 2 infusion-related reaction, the infusion rate of Durvalumab, Tremelimumab, Oleclumab or monalizumab may be decreased by 50% or interrupted until resolution of the event (up to 4 hours) and re-initiated at 50% of the initial rate until completion of the infusion. In subjects experiencing Grade \leq 2 infusion-related reaction, subsequent infusions may be administered at 50% of the initial rate.

Primary prophylaxis against infusion-related reactions is not permitted during this study in order to avoid obscuring a potential safety signal and enable a future assessment regarding whether premedications should be required for all subjects in future studies. However, at the discretion of the investigator, secondary prophylaxis (ie, prevention of infusion-related reaction following initial episode) is appropriate and will be permitted. Acetaminophen and/or an antihistamine (eg, diphenhydramine) or equivalent medications per institutional standard may be administered at the discretion of the investigator. If the infusion-related reaction is Grade 3 or higher in severity, treatment with Durvalumab, tremelimumab, Oleclumab and monalizumab will be discontinued.

As with any mAb, allergic reactions to dose administration are possible. Therefore, appropriate drugs and medical equipment to treat acute anaphylactic reactions must be immediately available, and study personnel must be trained to recognize and treat anaphylaxis.

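### The 48-hour definition of an infusion reaction puts some drug-related Grade 3+ events under both a discontinuation rule and a hold-and-resume rule, and makes the reaction count non-specific

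*Combined protocol and SAP*

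**What the plan says.** **Definition.** Section 7.3.3 opens with "Adverse events of infusion reactions (also termed infusion-related reactions) are of special interest to the supporting company" and defines them, for this protocol, as "all AEs occurring from the start of the study treatment infusion up to 48 hours after the infusion start time". The only condition is time.

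**Description elsewhere.** The infusion-related part of Table 7.7.1 describes these reactions by signs and symptoms such as fever, chills, flushing, itching and changes in heart rate or blood pressure. Section 7.4 places them during or soon after exposure and asks the investigator to weigh symptoms before settling on a diagnosis.

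**Consequence.** Section 8.1.5: "If the infusion-related reaction is Grade 3 or higher in severity, treatment with Durvalumab, tremelimumab, Oleclumab and monalizumab will be discontinued". For Grade 3 or 4, the infusion-related part of Table 7.7.1 says "Permanently discontinue study drug/study regimen".

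**Other instructions for Grade 3+ events.** The general part of Table 7.7.1 says of asymptomatic amylase or lipase of Grade 3 or above that, after a hold, "if complete work up shows no evidence of pancreatitis, study drug/study regimen may be continued or resumed". Other rows allow hold-and-resume for Grade 3 transaminase elevations up to 8 times the upper limit of normal, Grade 3 rash and Grade 3 non-immune-mediated events.

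**Exemptions for unrelated events.** Section 7.3: "These guidelines apply to AEs considered causally related to the study drug/study regimen by the reporting investigator". Section 7.7: "Treatment modifications will not be required for AEs that are clearly not attributed to Durvalumab, tremelimumab, oleclumab or Monalizumab", with an accident as its example. The non-immune part of Table 7.7.1: "Dose modifications are not required for AEs not deemed to be related to study treatment".

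**The concern.** The protocol uses one term for two things. In Section 7.3.3 it is a time window. In Table 7.7.1 and Section 7.4 it is a clinical reaction. A stopping rule is attached to the term, so the meaning applied can decide whether a patient keeps adjuvant immunotherapy after a given event.

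The second stake is the safety report. Safety is a primary endpoint (Section 13.1), and infusion-related reactions are events of special interest (Section 7.3). Section 8.1.5 bars primary prophylaxis so that a safety signal is not hidden and the need for premedication in later studies can be judged. A count of every adverse event in a time window does not measure infusion tolerability. It also grows with the number of infusion days, which differs between cohorts.

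**Working it through.** The documents state no infusion-reaction rate, so there is no figure to reproduce. The check is a comparison of the text, followed by one simple division.

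**Step 1: which instructions reach the same event.** Take a Grade 3 event that the investigator considers related to study drug and that starts within 48 hours of the start of an infusion. Under Section 7.3.3 it is an infusion-related reaction.

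| Event (related, Grade 3 unless stated) | As an infusion-related reaction (8.1.5, Table 7.7.1) | Under its own row of Table 7.7.1 |
|---|---|---|
| Rash | discontinue | hold; discontinue permanently only if not improved to Grade 1 or less, or baseline, within 30 days |
| Transaminases up to 8 × ULN | discontinue | hold; resume if Grade 1 or less, or baseline, within 14 days and after steroid taper |
| Non-immune-mediated event | discontinue | hold; resume if Grade 2 or less within 7 days, or Grade 1 or less, or baseline, within 14 days |
| Asymptomatic amylase or lipase, Grade 3 or above, judged a reportable adverse event | discontinue | hold; may continue or resume if the work-up shows no pancreatitis |

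These events are drug-related, so the exemptions for unrelated events do not remove the conflict. No text says which instruction takes precedence.

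**Step 2: unrelated events.** Sections 7.3 and 7.7 and the non-immune part of Table 7.7.1 exempt them. Section 8.1.5 lies outside Section 7.7 and has no attribution qualifier. Read literally with Section 7.3.3, it conflicts with those exemptions.

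**Step 3: the stopping rules.** TOX (Section 13.3.2) and TOXpost (Section 13.3.3) require a possible, probable or definite relation to protocol therapy. Neither uses the 48-hour definition.

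**Step 4: coincidental events in the count.** Assume that events unrelated to the infusion are spread evenly over the adjuvant dosing interval. The share captured is window length divided by dosing interval.

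- Cohorts A and C, infusions every 4 weeks: 2/28 = 7.1%.
- Cohort B, oleclumab every 2 weeks: 2/14 = 14.3%.
- Ratio: 14.3/7.1 ≈ 2.

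This ratio applies to the coincidental component only. Write G for genuine reactions (taken as equal across cohorts) and C for coincidental events captured in Cohort A or C over the same adjuvant time. The ratio of total counts is then (G + 2C)/(G + C), which lies between 1 and 2. The documents give neither G nor C, so the total cannot be computed.

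**Step 5: the whole treatment course.** Each cohort has one neoadjuvant infusion day. For patients who complete adjuvant immunotherapy, Cohorts A and C have 1 + 4 = 5 infusion days. Cohort B has 1 + 8 = 9 if fortnightly dosing runs from week 1 to week 15 in Table 10.3, giving 9/5 = 1.8. If the oleclumab row of that table is read as seven days, the ratio is (1 + 7)/5 = 1.6.

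**The case against.** The best defence is that Section 7.3.3 is a reporting definition. Its stated consequences are completion of the case report form and reporting of serious events. Management is referred to Section 7.7, where the reactions are described by symptoms, and Section 8.1.5 deals with slowing, interrupting and restarting an infusion. On this view no investigator would carry the reporting window into the stopping rule. This has weight as a prediction of practice. It does not settle the text, because Section 7.3.3 equates the two terms and gives its definition for the whole protocol.

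A reader might infer that any unrelated Grade 3 event in the window, even an accident, forces permanent discontinuation. The documents do not support that. Sections 7.3 and 7.7 and Table 7.7.1 exempt events not attributed to study drug, and Section 7.7 names an accident. What remains is the missing qualifier in Section 8.1.5.

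The amylase and lipase example also needs care. Section 7.1 says that laboratory values that are neither medically significant nor in need of intervention should not be reported as adverse events, and Section 7.7 exempts those not deemed clinically significant. Only a rise judged reportable and related is in doubt.

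The statistical reach is modest. No infusion-reaction rate is a named endpoint, and Section 13.4 says only that adverse events will be tabulated, with no formal hypothesis tests. Adverse events are collected from consent to 90 days after the last durvalumab dose (Section 7.4.1), so the window covers a smaller share of all collected events than of an adjuvant interval. Patients who choose postoperative chemotherapy (Section 5.1) have no extra infusion days in any cohort. All of this stands and limits the size of the point.

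**Conclusion.** The point holds in a limited form. A drug-related Grade 3+ event that starts within 48 hours of an infusion can receive opposite instructions on study drug, with no stated precedence. Section 8.1.5 also lacks the attribution condition found elsewhere. The special-interest count under the literal definition mixes genuine reactions with coincidental events.

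If coincidental events are evenly spread, the window covers about 7% of a 4-week and 14% of a 2-week adjuvant interval. That about doubles the coincidental component in Cohort B during adjuvant treatment. Over a full course the ratio is 1.6 to 1.8, depending on how Table 10.3 is read. It would be tempting to conclude that Cohort B's overall infusion-reaction rate doubles with no true difference. That is not shown, because the documents give no background event rate and the genuine component need not follow the same ratio.

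The primary feasibility analysis and the TOX and TOXpost boundaries do not rest on this definition. The effect is on individual treatment decisions and on the interpretation of one safety tabulation. The change should be made, but it is not critical to the design.

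**What to change.** 1. Reconcile Sections 7.3.3 and 8.1.5 and Table 7.7.1 so that the term has one meaning wherever a treatment consequence is attached to it. State which instruction governs when a Grade 3+ event starts within 48 hours of an infusion, and whether the exemption for unattributed events applies to Section 8.1.5. These are clinical decisions for the sponsor and investigator, and this review does not say which rule is right.
2. Keep the 48-hour window as a flag on the adverse event record.
3. Tabulate adverse events within 48 hours of an infusion separately from investigator-assessed infusion-related reactions, by cohort. Give the number of infusions beside each count so that the different schedules are visible.

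The cost is small: wording changes in the protocol, one data flag and one extra table. Reported infusion-reaction counts will be lower than under the literal definition, and the report should explain why.
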